### **7. Safety Assessments**

#### **7.1 Adverse Events and Serious Adverse Events**

Adverse Event: An AE is any untoward medical occurrence in a patient administered a study product and which does not necessarily have a causal relationship to the study product. Patients will be instructed to contact the Study Team at any time if any symptoms develop.

Serious Adverse Event: An SAE is an event that:

- Results in death
- Is immediately life threatening
- Requires inpatient hospitalization or prolongs existing hospitalization
- Results in persistent or significant disability and/or incapacity, or
- Is a congenital anomaly/birth defect

An important medical event that may not result in death, be life threatening, or require hospitalization may be considered an SAE when, based upon appropriate medical judgment, it may jeopardize the patient and may require medical or surgical intervention to prevent one of the outcomes listed in this definition. Examples of such medical events include allergic bronchospasm requiring intensive treatment in an emergency room or at home, blood dyscrasias or convulsions that do not result in inpatient hospitalization, or the development of drug dependency or drug abuse.

At every study visit, patients will be asked questions to elicit medically related changes in their well-being. They will also be asked if they have been hospitalized, had any accidents, used any new medications, or changed concomitant medication regimens. Any difference in responses to any question on the side effects questionnaire between visits will not be considered an adverse event unless the subject verbally informs the research team.

## **7.2 Reporting Procedures**

All AEs observed from the time the patient receives the first treatment until the last follow-up visit will be recorded on the CRF. The description of the AE will include the type of event, onset date, assessment of severity, date of resolution of event, seriousness, any required treatment of evaluations, and outcome.

All SAEs will be reported to the Beth Israel Deaconess Medical Center Institutional Review Board (IRB). In addition, the FDA will be notified of all serious and unexpected AEs in an IND safety report no later than 15 calendar days after awareness of the event and 7 days after a suspected unexpected serious adverse event that results in death.

A formal report from the DSMB will be supplied to NCCIH, which will be communicated to the PI and the Beth Israel Deaconess Medical Center. Each report will conclude with a recommendation to either 1) continue the study without changes; 2) continue the study with changes; or 3) terminate the study. This recommendation will be made by formal majority vote and fully justified by the preceding report.

Any AEs observed that are unanticipated will be reported under the following schedule:

1. Unanticipated problems that are serious adverse events will be reported to the IRB within 1 week of the investigator becoming aware of the event.
2. Any other unanticipated problem will be reported to the IRB within 2 weeks of the investigator becoming aware of the problem.

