#### **4. Selection and Enrollment of Participants**

Approximately 313 IBS patients who meet all of the inclusion criteria and none of the exclusion criteria will be enrolled.

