### **5. Study Interventions**

#### **5.1 Interventions, Administration, and Duration**

The study involves four groups as follows:

- open-label placebo 1 softgel TID (N~80)
- double-blind placebo 1 softgel TID (N~80)
- double-blind peppermint oil 1 softgel TID (N~40)
- no additional treatment control (N~80)

Placebo will be supplied as soybean oil (manufactured by SoftGel Technologies Inc.), matched to peppermint oil softgels (Pepogest™). The open-label and double-blind placebo are identical and both are matched to the peppermint oil. Each peppermint oil dose is 0.2mL. Study drug should be administered approximately 30 minutes before meal times.

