### 6.2.2 Follow-up Visits

**Visits 2 and 3:** At these visits, the following procedures will be performed: vital signs (Visit 3 only), brief physical examination with clinician interaction, dispensation of pills (if appropriate), pill counts (if appropriate), review of concomitant medications, and documentation of adverse events. A research coordinator will assist in completion of questionnaires and collection of blood. Whenever possible, the same treatment provider will see the patient for all visits.

Vital signs will not be recorded in the source documents, as they are done to mirror a standard clinic visit from the subject perspective and will not be analyzed.

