## **8. Statistical Considerations**

### **8.1 Randomization**

Treatment assignments will be generated using permuted block randomization with randomly varying block sizes. Randomization will be done in a 2:2:2:1: ratio (open-label placebo; double-blind placebo; no treatment control; double blind peppermint oil). Randomization for the qualitative sub-study will be done. Randomized assignments to one of the four groups will be sealed in sequentially numbered opaque envelopes.

A random subset of approximately 57 of the participants will be selected for participation in the nested qualitative study. The participants will be randomly selected in the same ratio as the primary randomization. Care providers will be blinded to participation in the sub study. A list of selected randomization IDs and access to the REDCap patient scheduling module will be provided to the interviewer so that he or she can conduct the qualitative interview after the participant has completed the final clinical evaluation.

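### The adverse-event definition and recording start (Sections 7.1 and 7.2) depend on receiving a study product, which does not fit the no-additional-treatment arm and contradicts the all-patient AE schedule

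*Combined protocol and SAP*

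**What the plan says.** Two statements govern what counts as an AE and what is recorded. Section 7.1: "An AE is any untoward medical occurrence in a patient administered a study product". Section 7.2: "All AEs observed from the time the patient receives the first treatment until the last follow-up visit will be recorded on the CRF". Neither offers another starting point, such as consent or randomisation, for a patient who is given no product.

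Section 5.1 lists four arms. Three take a softgel three times a day; the fourth, with about 80 patients, takes none.

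Other sections collect AEs from everyone. Section 7.1 itself says: "At every study visit, patients will be asked questions to elicit medically related changes in their well-being". Section 6.2.2 lists for Visits 2 and 3 "dispensation of pills (if appropriate), pill counts (if appropriate), review of concomitant medications, and documentation of adverse events". The schedule in Section 6.1 marks AEs at Weeks 3 and 6, and Appendix 3 lists the AE log at Visits 2 and 3, both without an exception for any arm.

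**The concern.** The definition and the recording window share a condition that one large arm can never meet. A coordinator told of a migraine in a control patient at Visit 2 has a scheduled AE log to complete and a definition that excludes the event. The protocol does not say which prevails.

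The risk is recording that differs by arm. Section 6.2.4 blinds the clinician only between peppermint oil and double-blind placebo, so the clinician can know who is on open-label placebo and who is in the control arm. The assessor who gives the questionnaires is blinded to all groups, but Section 6.2.2 places AE documentation in the clinician visit and does not say who does it.

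The no-additional-treatment arm shows the background rate of symptoms against which AEs on placebo would be read. If its events are recorded less completely, ordinary background symptoms on placebo can look like effects of the softgel. Section 7.2 also has the DSMB recommend whether to continue, change or terminate the study.

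**Working it through.** **1. Size of the affected group.** Section 5.1: 80 + 80 + 40 + 80 = 280 patients, and 80/280 = 2/7 = 28.6%. Section 8.1 gives the ratio 2:2:2:1, which is also 2/7. With the enrolment of 313 in Section 4, 313 × 2/7 = 89.4. Section 8.4 uses 88 per group. The arm therefore has about 80 to 89 patients.

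**2. The passages side by side.**

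| Question | Sections 7.1 and 7.2, as rules | Sections 6.1, 6.2.2, 7.1 (visit questions) and Appendix 3 |
|---|---|---|
| Whose events are AEs? | Patients given a study product | No restriction by arm |
| When does recording start? | At first treatment | AEs documented at Visits 2 and 3 |
| Control arm covered? | No | Yes |

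In Section 6.2.2 the qualifier about appropriateness is attached to dispensing and counting pills, not to AE documentation. That points to an intention to document AEs in every arm.

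Could first treatment be read as assignment to the control condition? The definition in Section 7.1 blocks this, because it requires that a product was administered.

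**3. The interval before the first dose.** Section 6.2.1 requires every assessment except blood collection to precede randomisation. An event from a blood draw made after randomisation but before the first softgel falls outside the Section 7.2 window in every arm. This interval is probably short, so the point is secondary.

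**4. Direction and possible size of bias.** The plan states no AE rate and no AE test, so there is no figure to reproduce. Suppose the true AE rate is *p* in both arms, all events on open-label placebo are recorded, and a fraction *r* of control-arm events is recorded. The expected apparent difference is *p* − *rp* = *p*(1 − *r*). It is zero when *r* = 1 and greatest, at *p*, when *r* = 0.

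Worst case only (*r* = 0): with *x* events out of *n* against 0 out of *n*, the two-sided Fisher exact probability is 2 × C(*n*, *x*) / C(2*n*, *x*). For *n* = 80 and *x* = 4 this is 2 × (80·79·78·77)/(160·159·158·157) = 2 × 0.0601 = 0.12.

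| Assumed AE rate | *n* = 80: events, p | *n* = 89: events (rounded), p |
|---|---|---|
| 5% | 4 v 0, 0.12 | 4 v 0, 0.12 |
| 10% | 8 v 0, 0.0065 | 9 v 0, 0.0032 |
| 20% | 16 v 0, 0.000013 | 18 v 0, 0.0000029 |

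These figures show what complete non-recording could do under assumed rates. They do not predict this trial's results.

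**The case against.** The strongest reply is that the operational text already collects AEs in every arm: patients are questioned at each visit, Section 6.2.2 documents AEs without a qualifier, and the AE log is scheduled for everyone. On that view, Sections 7.1 and 7.2 merely use standard wording for a drug trial. Much of this stands. A reader might infer that the control arm is bound to show no AEs; the documents do not support that, because they schedule the collection. But a schedule says when to ask, while Sections 7.1 and 7.2 say what counts and what is entered on the CRF. Evident intent does not remove the contradiction.

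A reader might also infer that a planned safety comparison of placebo with no treatment is invalid. Section 8 contains no such comparison; Aims 1, 1a and 1b concern clinical outcome. Nor do the documents say that the DSMB reviews AEs by arm. Only a descriptive table by arm, or a review that used one, could be distorted.

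A third inference, that SAEs in the control arm would be lost, also goes too far. The SAE definition in Section 7.1 carries no product condition of its own, Section 7.2 sends all SAEs to the IRB, and patients are asked about hospitalisation. Control-arm SAEs drop out only if the product condition is carried over from the AE definition.

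Finally, the side effects questionnaire at Visits 1 and 3 gives symptom data in all arms. That is useful, but under Section 7.1 a changed answer is not an AE unless the patient also reports it verbally, so it does not replace AE recording.

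**Conclusion.** The concern holds as an internal contradiction that should be corrected. The stated definition and recording start exclude 2/7 of randomised patients (about 80 to 89), while the visit procedures include them. If staff followed Sections 7.1 and 7.2 literally, even in part, AE capture would be asymmetric and descriptive safety results would lean against the softgel arms.

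How far depends on two things the documents do not give: the background AE rate, and how completely control-arm events would be recorded. If the visit schedule is followed in full, there need be no bias from this source. The Fisher figures rest on assumed equal rates, total non-recording in the control arm and a test that is not planned, so they mark only the worst case. The efficacy analyses do not depend on this wording.

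**What to change.** Reconcile Sections 7.1 and 7.2 with Sections 6.1 and 6.2.2 and Appendix 3:

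- In Section 7.1, define an AE as any untoward medical event in a randomised patient, whether or not a study product was given.
- In Section 7.2, record AEs and SAEs from randomisation at Visit 1 to the last follow-up visit in all four arms, and tabulate them by arm over that common window.

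This also covers events between randomisation and the first softgel, and makes clear that control-arm SAEs are included. It needs two wording changes and no new visit or form, since the AE log is already scheduled for every patient. The downside is a few more AE entries. The change is best made before data accumulate, because events not recorded at the time may be hard to recover.

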## **8. Statistical Considerations**

### **8.1 Randomization**

Treatment assignments will be generated using permuted block randomization with randomly varying block sizes. Randomization will be done in a 2:2:2:1: ratio (open-label placebo; double-blind placebo; no treatment control; double blind peppermint oil). Randomization for the qualitative sub-study will be done. Randomized assignments to one of the four groups will be sealed in sequentially numbered opaque envelopes.

A random subset of approximately 57 of the participants will be selected for participation in the nested qualitative study. The participants will be randomly selected in the same ratio as the primary randomization. Care providers will be blinded to participation in the sub study. A list of selected randomization IDs and access to the REDCap patient scheduling module will be provided to the interviewer so that he or she can conduct the qualitative interview after the participant has completed the final clinical evaluation.

### **8.2 Stratification**

Stratification will be based on IBS symptom severity score (< 300 and ≥ 300) and gender, resulting in 4 strata. Each stratum will have a different color randomization envelope and a unique set of randomization ID numbers.

### 8.3 Analyses

All tests will be two-tailed with  $\alpha=.05$ . For our primary analyses, we will use a modified intention-to-treat analysis including any patient who was randomized and provided a baseline assessment and at least one post-baseline primary outcome assessment. We will also run per protocol analyses, and any substantive differences between the two methods will be reported.

We will examine the amount of missing data and the nature of the missingness (missing completely at random, missing at random, and missing not a random). If necessary, we will conduct a full intention to treat analysis.

**Aim 1.** To determine whether 6 weeks of open-label placebo, double-blind placebo and no-treatment results in different clinical outcomes. To test this aim, we will conduct a one-way analysis of covariance. In addition to treatment group, the model will include baseline IBS-SSS and stratification factors for gender and symptom severity.

Assuming that there is a significant difference between the 3 groups, Dunnett's analysis will be used to do pairwise analyses of the following aims

**1a.** To determine if 6 weeks of open-label placebo results in superior clinical outcome than no treatment control. Hypothesis: open-label placebo > no treatment control.

**1b.** To determine if 6 weeks of open-label placebo results in superior clinical outcome than double blind placebo. Hypothesis: open-label placebo > double-blind placebo.

**Secondary Aims Analysis Plan:** There are three secondary multi-disciplinary aims in this study.

**Secondary Aim 1 (Genetics Aim):** In our previous large RCT we found that the number methionine alleles in COMT val158met was associated with placebo responses especially to a combined placebo and supportive patient-provider relationship. We plan to confirm these findings and extend them by evaluating additional candidate genes implicated in placebo. Exploratory analyses will be performed in other candidate genes associated with placebo including: the mu-opioid receptor polymorphism (OPRM1 A118G), FAAH polymorphisms Pro129Thr. monoamine oxidase gene polymorphisms, and serotonin-related polymorphism CGTTLPR and G-703T (polymorphism in the tryptophan hydroxylase-2 (TPH-2) gene promoter).

DNA will be extracted from those study participants who agree to the genetic screening and will be analyzed by a TaqMan allele discrimination assay. Subsequently, COMT and other candidate genotypes will be correlated with response to placebo or active drug treatment using the above mentioned outcomes. Furthermore, potential correlations of the COMT and other genotypes and patient-disease characteristics, for instance pain experience at baseline, will be examined.

**Secondary Aim 2 (Psychological Aim):** In our previous large RCT in IBS we found that higher levels of extraversion, agreeableness, and openness to experience are associated with increased response to placebo treatment, especially with an augmented patient-practitioner relationship. We will use the Five Factor Inventory (FFI) to measure these personality traits and

then use multiple regression to examine their association with outcomes after controlling for baseline severity.

**Secondary (exploratory) Aim:** To determine if 6 weeks of double-blind peppermint oil results in greater improvement than double-blind placebo in patients with IBS. Hypothesis: Double-blind peppermint oil > Double-blind placebo. To test this aim, we will conduct an analysis of covariance. In addition to treatment group, the model will include baseline IBS-SSS and stratification factors for gender and symptom severity.

**8.4 Power Calculations:** To estimate the effect size for Aim 1, we used our previous pilot trial in IBS. In that study, the effect size for the difference between open-label placebo and no-treatment on the IBS Symptom Severity Scale was  $d=0.53$ . For this comparison, there will be 88 patients in each group, and using ANCOVA to control for baseline scores leaves the power for the 3 group comparison at .96. To estimate the power for secondary (exploratory) aim using ANCOVA to control baseline scores leaves the power of .60; however, using more recent data that suggest an effect size of  $d=0.50$ , the power would be .78.

**8.5 Missing Data Minimization Strategies:** Missing data minimization strategies includes patient retention efforts and a modified intent-to-treat analysis. Each individual patient reported assessment will be captured electronically at each visit with missing responses prohibited by the electronic system.

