## **1. Study Objectives**

### **1.1 Primary Objectives**

The primary objectives of this study are to: (1) to determine whether 6 weeks of open-label placebo, double-blind placebo and no additional treatment control results in different clinical outcomes in patients with IBS and (2) assuming there are significant differences (a) to determine whether open-label placebo results in greater clinical improvement compared to no additional treatment control and (b) to determine if open-label placebo results in greater clinical outcome than double blind placebo.

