#### 3.2 Efficacy Assessments

##### Primary Outcome Measure

The primary outcome measure is the IBS symptom severity scale (IBS-SSS). The IBS-SSS is a questionnaire that measures the sum of the participant's evaluation on a 100 point scale of each of five items: severity of abdominal pain, frequency of abdominal pain, severity of abdominal distension, dissatisfaction with bowel habits, and interference with quality of life. All five components contribute equally to the score, yielding a theoretical range of 0-500, in which a higher score indicates a more severe condition. The responder will be considered a patient who has at least a 50 point decrease in their IBS-SSS from baseline to Visit 3. Using data from our previous IBS trial the calculated Cronbach's alpha is .70.

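### The primary set admits patients with only a Week 3 IBS-SSS, but the 6-week ANCOVA has no outcome for them and the plan gives no rule for a missing Week 6 score

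*Combined protocol and SAP*

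**What the plan says.** **Analysis set (8.3).** The primary analysis is a modified intention-to-treat analysis of "any patient who was randomized and provided a baseline assessment and at least one post-baseline primary outcome assessment". Appendix 3 schedules IBS-SSS at Visits 1, 2 and 3, and the schedule in 6.1 places Visits 2 and 3 at Weeks 3 and 6.

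**Time point.** The first primary objective (1.1) is "to determine whether 6 weeks of open-label placebo, double-blind placebo and no additional treatment control results in different clinical outcomes". Section 3.2 defines a responder by "at least a 50 point decrease in their IBS-SSS from baseline to Visit 3".

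**Model (8.3, Aim 1).** "To test this aim, we will conduct a one-way analysis of covariance". The terms are treatment group, baseline IBS-SSS, gender and severity stratum. The dependent variable is not named.

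**Missing data.** Section 8.3 says "We will examine the amount of missing data and the nature of the missingness", and then "If necessary, we will conduct a full intention to treat analysis". It also plans per-protocol analyses, with substantive differences reported. Section 8.5 says "Missing data minimization strategies includes patient retention efforts and a modified intent-to-treat analysis", and adds that the electronic system will not accept blank responses. Section 6.2.5 says that data collection will be attempted whatever the patient's compliance, with no extra procedures for those who stop early.

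**The concern.** The declared set and the declared model do not fit together. A patient seen at Week 3 and then lost belongs to the set but has no 6-week outcome for a single-time-point ANCOVA. The plan does not say which gives way. If the software simply drops the patient, the primary analysis is a Week 6 completer analysis of a smaller set than the one declared. If a value is supplied, the method could be chosen after the data are seen.

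The key comparison, open-label placebo against no treatment, is exposed to this. Patients in both arms know their assignment and report the outcome themselves, so loss between Week 3 and Week 6 could differ by arm. If it does, and if leaving depends on how symptoms have changed, the Aim 1a estimate depends on the handling that the plan leaves open.

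**Working it through.** **1. Textual check**

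| Question | Where | Answer |
|---|---|---|
| Does a Week 3 score alone qualify? | 8.3, Appendix 3 | Yes |
| Which time point is primary? | 1.1, 8.3, 3.2 | 6 weeks (inferred; the outcome variable is not named) |
| Does the model use Week 3 scores? | 8.3 | No visit term, no Week 3 term |
| Is there a rule for an absent Week 6 score? | 8.3, 8.5, 6.2.5 | None |
| Trigger and method for full intention-to-treat? | 8.3 | Neither stated |

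The electronic bar in 8.5 concerns responses at a visit and cannot fill a missed visit. Appendix 3 also lists IBS-SSS among the paper source documents.

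**2. The plan's own figure**

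Section 8.4 takes d = 0.53 for open-label placebo against no treatment from the earlier pilot trial, with 88 per group, and states power .96 for the three-group comparison. With means (0, 0, 0.53), one covariate and no gain from baseline, the noncentrality is 88 × 0.53² × 2/3 = 16.48 on 2 and 3 × 88 − 4 = 260 degrees of freedom. Power is 0.960, so the figure reproduces. The plan gives neither the third group's mean nor the baseline correlation, so its exact route is unknown. The figure is not in dispute.

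No loss rate is stated. Assuming equal loss of 10% or 20% (79 or 70 left per group), the same formula gives 0.938 or 0.906. The power cost is modest.

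**3. Illustration of bias**

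From the documents: d = 0.53, with no time point given. Everything else is assumed:
- 0.53 SD is the true Week 6 effect, and the Week 3 effect is 0.30 SD.
- No-treatment patients improve by 0.3 SD at both visits.
- Baseline correlates .5 with each later visit, and Week 3 correlates .7 with Week 6.
- logit P(Week 6 missing) = a(arm) + s × Week 3 change, with a(arm) set to give the stated loss. The size of s is 0.7 to 1.5 per SD, an odds ratio of about 2.0 to 4.5. Its sign decides whether worse-off or improved patients leave.

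Two analyses are compared:
- *Completers*: ANCOVA of Week 6 on arm and baseline, in patients with a Week 6 score.
- *Likelihood using Week 3*: effect = b + g × c. Here b and g are the arm and Week 3 coefficients for Week 6 given baseline, estimated where Week 6 is observed. The term c is the arm effect at Week 3 given baseline, in everyone with a Week 3 score.

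Under these inputs g = (0.7 − 0.5 × 0.5)/(1 − 0.5²) = 0.45/0.75 = 0.6, c = 0.30 and b = 0.53 − 0.6 × 0.30 = 0.35. The total is 0.35 + 0.18 = 0.53. Loss that depends only on baseline and Week 3 leaves b, g and c unchanged, so this estimate stays at 0.53.

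Large-sample simulation (800,000 per arm, strata omitted), effect in SD:

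| Loss, open-label vs no treatment | Completers, worse-off leave | Completers, improved leave | Likelihood |
|---|---|---|---|
| 10% vs 10% | 0.53 | 0.53 | 0.53 |
| 5% vs 10% | 0.50-0.52 | 0.54-0.56 | 0.53 |
| 15% vs 5% | 0.56-0.58 | 0.48-0.50 | 0.53 |

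Carrying the Week 3 score forward is another rule the plan does not exclude. At 15% vs 5% with worse-off patients leaving, it gives 0.468-0.483, on the other side of the truth from completers.

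**4. If loss depends on the unseen Week 6 change** (worse-off leave)

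| Loss | Completers | Likelihood |
|---|---|---|
| 5% vs 10% | 0.487-0.505 | 0.502-0.514 |
| 15% vs 5% | 0.582-0.615 | 0.565-0.587 |

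Likelihood is now biased too, but less than completers.

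**The case against.** **The plan does address missing data.** It seeks data regardless of compliance, works on retention, examines missingness, and compares the primary analysis with per-protocol results. That is fair, and it would be wrong to call the plan silent. None of it says what the primary model does with a missing Week 6 score.

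**The effect may be small.** This stands. Equal loss gives no material bias. At 5% vs 10% with worse-off patients leaving, completers move by only about 0.01 to 0.03 SD. Larger shifts need a large imbalance arising within three weeks. All lost patients in the illustration leave after Week 3. Patients with no post-baseline score are outside the set, and the two-visit model adds almost nothing for them.

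**The preferred model is not always closest.** Also true. When loss depends on the unseen Week 6 change, carry-forward gives 0.514-0.522 at 15% vs 5%, closer to 0.53 than likelihood. That comes from offsetting errors under these inputs and is no reason to rely on it.

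**Three stronger readings are not supported.**
- A reader might infer that completers flatter open-label placebo, or penalise it. The direction depends on which arm loses more and on who leaves, and the documents settle neither.
- A reader might infer that examining missingness could never trigger the full analysis. Its amount and its imbalance by arm are observable and could define a trigger. Only missing at random versus not at random cannot be told apart from the data, so the examination cannot fully settle the method.
- A reader might infer from 6.2.5 that early discontinuers are not asked for a Week 6 score. It rules out only additional procedures, and the Week 6 IBS-SSS is already scheduled, so the natural reading is that it is still sought. A clarifying sentence would be optional.

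**Conclusion.** The mismatch is in the text and needs no simulation: the set is wider than the model can analyse, no rule covers a missing Week 6 score, and the full intention-to-treat fallback has no trigger or method. One inference is involved, that Week 6 IBS-SSS is the dependent variable. It rests on the 6-week wording and on the responder definition. If Week 3 scores were meant to count, that is unstated as well.

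The size is conditional. Under the assumed inputs, completer bias is up to about 0.03 SD either way at 5% vs 10% loss and about 0.03 to 0.05 SD either way at 15% vs 5%. It is essentially nil with equal loss arising in the same way. These figures illustrate sensitivity and do not forecast this trial. The point should be fixed because the remedy is cheap and uses scores already collected. It does not show that the trial's conclusion would be wrong.

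**What to change.** Before unblinding, amend 8.3 as follows.

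1. **Primary Aim 1 analysis.** Use a repeated-measures likelihood model of IBS-SSS at Weeks 3 and 6, with arm, visit, arm-by-visit, baseline, baseline-by-visit, gender and severity stratum, and unstructured covariance. Take the three-arm test and the planned pairwise contrasts at Week 6. Every patient in the declared set then contributes. An alternative with the same aim is to keep the ANCOVA after multiple imputation of Week 6 by arm from baseline and Week 3.
2. **Sensitivity analysis.** Replace the conditional full intention-to-treat sentence with a prespecified analysis of all randomised patients that shifts imputed Week 6 scores by arm, for example by 0 to 50 points. Fifty points is the responder threshold in 3.2. With 10% missing in an arm, it moves that arm's mean by 0.10 × 50 = 5 points.
3. **Minimum alternative.** If the plain ANCOVA is kept, name Week 6 IBS-SSS as its outcome and restate the set as patients with a Week 6 score. This removes the contradiction but leaves the possible completer bias.

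The cost is revised wording and a little more analysis work. The model and the imputation both rely on missing at random, and the shift analysis tests how far the result depends on that. With complete data the Week 6 contrast is essentially the planned ANCOVA, so little is given up.

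### Cheap improvement, not an error: naming step-down Dunnett in section 8.3 would make the tests of 1a and 1b less conservative without adding patients

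*Combined protocol and SAP*

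**What the plan says.** Section 1.1 makes the pairwise primary objectives conditional on the overall comparison: "assuming there are significant differences (a) to determine whether open-label placebo results in greater clinical improvement compared to no additional treatment control", followed by open-label versus double-blind placebo. Section 8.3 turns this into an analysis. For the overall aim, "To test this aim, we will conduct a one-way analysis of covariance" on the three groups, adjusted for baseline score and the two stratification factors. "All tests will be two-tailed" at .05. The pairwise step is then: "Assuming that there is a significant difference between the 3 groups, Dunnett's analysis will be used to do pairwise analyses of the following aims". The aims are 1a (open-label placebo versus no treatment) and 1b: "To determine if 6 weeks of open-label placebo results in superior clinical outcome than double blind placebo".

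No section says which form of Dunnett's procedure is meant. None names the common comparator, although 1a and 1b together imply open-label placebo.

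Section 8.4 gives d=0.53 as "the effect size for the difference between open-label placebo and no-treatment on the IBS Symptom Severity Scale was" in the pilot trial. It puts power at .96 on this basis: "there will be 88 patients in each group, and using ANCOVA to control for baseline scores leaves the power for the 3 group comparison". It gives no double-blind mean, no effect size for 1b and no power for 1b.

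**The concern.** With exactly three groups, 1a and 1b can both be null only if all three means are equal, and that is the hypothesis the ANCOVA has already tested at .05. Single-step Dunnett then guards against the same joint null a second time, by holding both contrasts to the stricter critical value.

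At stake is power for two primary questions, mainly 1b. The form of the procedure also changes decisions: whenever step-down rejects 1b and single-step does not, the same data give two verdicts. How often that happens is simply the power difference shown below; it is not a second, separate harm.

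**Working it through.** **Inputs from the documents.** Two-sided alpha .05, three groups, three covariates (baseline score, gender, severity stratum) and the gate (8.3); 88 per group and d=0.53 for open-label versus no treatment (8.4). Error degrees of freedom: 3×88 − 3 − 3 = 258.

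**Assumed, because not given.** The double-blind mean, in SD units above no treatment, varied from 0 to 0.53; the baseline-outcome correlation r, from 0 to 0.5; no dropout.

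**The plan's own figure.** Noncentrality of the three-group test is λ = n·Σ(μ − mean)²/(1 − r²).
- Double-blind equal to either extreme, r=0: 88 × 0.18727 = 16.48, power .960.
- Double-blind midway (0.265), r=0.5: 88 × 0.14045/0.75 = 16.48, power .960.

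The stated .96 reproduces, but from quite different configurations, so it does not reveal the double-blind mean.

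**Critical values at 258 df.** F = 3.031; unadjusted t = 1.969; two-sided Dunnett for two contrasts with correlation 0.5 = 2.224. A contrast tested against 2.224 is tested at about .027.

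**Rules compared, both behind the F gate.**
- Single-step: each |t| > 2.224.
- Step-down: larger |t| > 2.224, then the other > 1.969.

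**Error rate on 1a/1b (simulated, single-step / step-down).**
- All three means equal: .037 / .037.
- One true null, the other effect 0.53: .027 / .046 at r=0, with step-down about .048 at r=0.5.

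Step-down does not need the gate for this. If both nulls hold, the larger |t| exceeds 2.224 with probability .05. If one holds, its own |t| exceeds 1.969 with probability .05. The gate can only lower these.

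**Power for 1b (simulated, single-step → step-down).**

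| Double-blind mean | 1b effect | r=0 | r=0.5 |
|---|---|---|---|
| 0 (equals no treatment) | 0.53 | .897 → .925 | .965 → .978 |
| 0.13 | 0.40 | .663 → .738 | .798 → .858 |
| 0.265 (midway) | 0.265 | .321 → .412 | .424 → .523 |
| 0.40 | 0.13 | .089 → .136 | .112 → .168 |

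**Hand check, midway.** The expected t is d·√(n/2)/√(1 − r²). At r=0 this is 0.265 × 6.633 = 1.758, so power is about Φ(1.758 − 2.224) = .32 against 2.224 and Φ(1.758 − 1.969) = .42 against 1.969. At r=0.5 it is 1.758/0.866 = 2.030, giving about .42 and .52.

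**Ceiling.** The critical values differ by 0.255, so the loss cannot exceed about 2Φ(0.1275) − 1 = .10. A grid over double-blind means from 0 to 0.53 and r from 0 to 0.5 gave at most 9.9 points, even against a fully unadjusted test.

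**Other yardsticks.**
- Smallest 1b difference with 80% power: 0.465 → 0.433 SD at r=0; 0.401 → 0.370 SD at r=0.5.
- 1a at r=0: .897 → .925 if double-blind equals no treatment; .877 → .880 midway; .896 → .898 if double-blind equals open-label.
- With the roughly 80 per arm listed in section 5.1, midway 1b is about .29 → .38 at r=0 and .39 → .48 at r=0.5.
- In the midway case, 80% power for 1b would need about 225 per group at r=0 (169 at r=0.5) even with an unadjusted .05 test.

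**The case against.** The strongest reply is that nothing here is wrong. Dunnett's procedure without qualification normally means single-step; it is valid with or without the gate, and its tests agree with its simultaneous intervals. A sponsor may reasonably prefer that. The largest gain also arises where 1b is underpowered anyway; where 1b is well powered, the gain is 1 to 3 points. All of this stands, and it is why the point is an improvement and not a defect.

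A reader might infer three stronger things that the documents do not support.
- *The plan fails to control the false-positive rate.* It does control it, under either form.
- *The choice of Dunnett is what leaves 1b underpowered.* It is not. Section 8.4 plans no effect or power for 1b, and in the midway case 88 per group is too few under any of these rules. That is a separate sample-size question.
- *The adjustment should be dropped and both contrasts tested at unadjusted .05 behind the gate.* With three groups this is valid, but familywise control then rests wholly on the gate and on there being exactly three groups. Step-down recovers nearly all of the 1b power without that dependence.

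What survives the reply is that step-down never rejects less than single-step, costs no patients, and is not ruled in or out by the current sentence.

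**Conclusion.** The analysis in section 8.3 is valid as written and, on its usual reading, more conservative than it needs to be. Step-down Dunnett would raise 1b power by about 1 to 3 points if double-blind placebo equals no treatment, 6 to 8 points at a double-blind mean of 0.13, and at most about 10 points near midway. If double-blind placebo equals open-label placebo, 1b is null and there is no power to gain. These sizes rest on 88 per group, d=0.53 for 1a, r between 0 and 0.5, no dropout and an assumed double-blind mean. The error-rate result and the ceiling of about 10 points do not depend on where the double-blind mean lies. It is worth a sentence in the plan, no more.

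**What to change.** In section 8.3, after the gate, specify: *step-down Dunnett with open-label placebo as the common comparator; the larger |t| of 1a and 1b is compared with the two-sided Dunnett critical value (about 2.22) and, if significant, the other with the two-sided .05 t value (about 1.97), both from the Aim 1 model; single-step Dunnett simultaneous 95% intervals are reported as supportive.*

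Fix this before anyone sees outcome data by arm. The condition matters because, under section 6.2.4, the clinician's blinding covers only peppermint oil versus placebo within the double-blind groups, and a later choice could be driven by the 1b result.

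The cost is one sentence: no patients, no new data, no change to the objectives. The downside is that a contrast can be declared significant while its simultaneous 95% interval includes zero. If matching intervals matter more to the sponsor, naming single-step and saying why also removes the ambiguity, at the power shown above.
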